4.9 Discontinuation of investigational product

An individual patient will not receive any further IP if any of the following occur in the patient in question:

- Withdrawal of consent from further treatment with IP. The patient is, at any time, free to discontinue treatment, without prejudice to further treatment. A patient who discontinues treatment is normally expected to continue to participate in the study unless they specifically withdraw their consent to further participation in any study procedures and assessments (see Section [4.10.2](#)).
- Any AE that meets criteria for discontinuation as defined in the Dosing Modification and Toxicity Management Guidelines (see study-specific information in sub-protocols). Note that this is arm specific; this would not impact enrollment into the other arms in the study.
- Initiation of alternative anticancer therapy including another investigational agent.
- AEs that, in the opinion of the Investigator or the Sponsor, contraindicate further dosing. Note that this is arm specific; this would not impact enrollment into the other arms in the study.
- Confirmed PD per RECIST 1.1 and Investigator determination that the patient is no longer benefiting from treatment with IP.
- Non-compliance with the study protocol that, in the opinion of the Investigator or AstraZeneca, warrants withdrawal from treatment with IP (eg, refusal to adhere to scheduled visits).
- Patients incorrectly initiated on study treatment (eg, patient is determined to have met 1 or more of the exclusion criteria for study participation at study entry and continuing investigational therapy might constitute a safety risk)
- Pregnancy or intent to become pregnant.

Should any of this occur, the patient will not receive any further IP.

If the patient is discontinued from study treatment, the scheduled study visits, data collection, and procedures should continue according to this study protocol until study closure of the arm the patient is participating in. Alternatively, if the patient does not agree to this option, a modified follow-up through methods such as regular telephone contacts or a contact at study closure should be arranged, if agreed to by the patient and in compliance with local data privacy laws/practices (see Section 4.9.2).

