4.6 Discontinuation of investigational product

See Section [4.9](#) of the master protocol.

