6.1.2 ECG

A 12-lead safety ECG (paper ECG printout of 10 seconds for Investigator review) will be taken at screening and prior to dosing on day 1 of each study cycle.

Triplicate ECG recordings should be taken within an approximate 5-minute period. Additional ECGs may be taken at any other time the Investigator deems necessary for safety during the administration period. The patients will rest for at least 10 minutes before the start of each recording and they must be in the same supine body position (maximum 30 degrees flexion in the hip and feet not in contact with the footboard) at the recording time point.

The Investigator will judge the overall interpretation as normal or abnormal. If abnormal, it will be decided as to whether or not the abnormality is clinically significant or not clinically significant. The paper copy of each ECG reading will be retained with the patient’s completed source documents. Only overall evaluation (normal/abnormal) will be recorded in the eCRF. If there is a clinically significant abnormal unscheduled ECG finding during the treatment

period, this should be recorded on the AE eCRF, according to standard AE collection and reporting processes (see Section 7).

Attention should be paid to any detected increases in QTc interval. Patients who develop a single resting value of QTc interval of >450 msec/male and >470 msec/female or a shift from baseline of ≥ 60 ms should stop taking AZD1775. Dosing can be resumed at a reduced dose after return of the resting QTc interval to pre-treatment status has been confirmed and correction of possible electrolyte imbalance has been made (see [Appendix B Table](#)).

Monitoring of QTc, checking and correction of abnormal electrolyte levels and renal function are advised, especially in case of severe/prolonged diarrhoea. If QTc increases markedly from baseline, but stays below the above limits, a cardiologist’s advice should be sought.

The concomitant use of ondansetron (known to prolong the QTc interval in rare cases, per labelling) should be taken into account when interpreting QTc changes.

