7.3.2 Dose modifications due to non-hematologic related adverse events

Dose modifications for non-hematologic toxicities should be based on toxicities occurring during the previous cycle. For toxicities that lead to a dose reduction, the dose will not be re-escalated during subsequent cycles.

Any patient who develops a Grade 3 or 4 non-hematologic toxicity that does not resolve to \leq Grade 1 within 28 days should be discontinued from the study treatment. However, if the Investigator determines that the non-hematologic toxicity was due to one study drug and not the other, treatment with the remaining study drug may continue as clinically appropriate.

Based upon the maximum non-hematologic toxicities experienced during the previous cycle, dose adjustments for subsequent cycles are to be made according to the criteria defined in [Appendix B Table 9](#) (unless specified per unique toxicities as noted below).

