Appendix B Table 9 Non-hematologic toxicity dose modification and management

Electrocardiogram QT corrected interval prolonged		
QTc Value	CBDP	AZD1775
QTc 450-480 ms (males) or 470-480 (females)	No dose modifications	Hold. Once QTc interval has returned to pretreatment status and correction of possible electrolyte imbalance has been made, resume at next lower dose level.
QTc 481-500 ms	No dose modifications	Hold. Seek cardiologist advice.

QTc \geq 501 ms	Discontinue treatment	Discontinue treatment
Shift from baseline of \geq 60ms	Discontinue treatment	Discontinue treatment
<hr/>		
CTCAE version 4.03	CBDP	AZD1775
Grade 0 - 2	No dose modification	No dose modification
Grade 3 ^{b,c,d}	Hold ^a	Hold ^a
Grade 4 ^b	Hold until toxicity resolves to Grade \leq 1. Resume with 1 dose level reduction	Hold until toxicity resolves to Grade \leq 1. Resume with 1 dose level reduction
Second repeat incidence of Grade 3 or 4 toxicity (except nausea, vomiting, fatigue, malaise, lethargy, anorexia, alopecia)	Discontinue treatment	Discontinue treatment
<hr/>		
Hepatic		
<hr/>		
CTCAE v4.03	CBDP	AZD1775
Grade 1-2	No dose modification	No dose modification
Grade 3 or 4 (manifested as elevations in ALT, AST, ALP, or bilirubin)	Hold until resolves to Grade \leq 1 or baseline, then resume CBDP with a 1 level dose reduction. If not resolved within 28 days, discontinue CBDP.	Hold until resolves to Grade \leq 1 or baseline, then resume study drug with a 1 level dose reduction. If not resolved within 28 days, discontinue study drug.
<hr/>		
Diarrhea or mucositis		
<hr/>		
CTCAE v4.03	CBDP	AZD1775
Grade 1-2	No dose modification	No dose modification
Grade 3 or 4 (or requiring hospitalization)	Hold ^a	Hold ^a
<hr/>		
Nephrotoxicity		
<hr/>		
CTCAE v4.03	CBDP	AZD1775
Grade 0-1	No dose modification	No dose modification

Grade ≥ 2 Hold until resolves to Grade ≤ 1 or Hold^a
baseline, then resume CBDP with
a 1 level dose reduction. If not
resolved within 28 days,
discontinue CBDP.

Neurotoxicity		
CTCAE v4.03	CBDP	AZD1775
Grade 1	No dose modification	No dose modification
Grade 2	Hold until toxicity resolves to Grade ≤ 1 . Resume with 1 dose level reduction.	No dose modification
Grade 3 or 4	Discontinue treatment	Discontinue treatment

- ^a Hold until toxicity resolves to \leq Grade 1 and then resume at the same dose with no modification.
- ^b Dose reduction for nausea and vomiting should be made only if Grade 3 or Grade 4 toxicity occurs in spite of maximum anti-emetics.

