7.3.3.6 QTc prolongation

The QTc interval will be measured in 12-lead ECGs at baseline and at the commencement of each treatment cycle; and an assessment made of the emergence, if any, of QTc prolongation. Serum electrolyte levels should be obtained at baseline and at commencement of each treatment cycle.

Checking and correction of abnormal electrolyte levels and renal function are advised, especially in case of diarrhoea.

The administration of AZD1775 with substances known to prolong the ECG QTc interval is not recommended.

Special note: The potential risk of concomitant use of AZD1775 with ondansetron (known to prolong the QTc interval) should be taken into account.

Dose modifications or discontinuations for patients experiencing QTc prolongations are summarized in [Appendix B Table](#) above.

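### Arm B: the ECG section allows AZD1775 to be restarted after a QTc shift of 60 ms or more, or a QTc of 501 ms or more, where Table 9 permanently discontinues both drugs

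*Protocol*

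**What the plan says.** Appendix B 6.1.2 (ECG) names two triggers for stopping AZD1775: a single resting QTc above 450 ms in men or 470 ms in women, and a shift from baseline of 60 ms or more. The next sentence covers both: "Dosing can be resumed at a reduced dose after return of the resting QTc interval to pre-treatment status has been confirmed", provided any electrolyte imbalance has also been corrected. The section does not mention carboplatin.

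Appendix B Table 9 divides QTc findings into four rows:
- At 450-480 ms in men or 470-480 ms in women, the AZD1775 instruction is "Hold. Once QTc interval has returned to pretreatment status and correction of possible electrolyte imbalance has been made, resume at next lower dose level".
- At 481-500 ms it is "Hold. Seek cardiologist advice".
- At 501 ms or more, both AZD1775 and carboplatin are discontinued.
- The row beginning "Shift from baseline of" 60 ms or more also discontinues both drugs.

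Appendix B 7.3.2 directs that non-hematologic dose adjustments follow Table 9, "unless specified per unique toxicities as noted below". The QTc paragraph that follows, 7.3.3.6, sends the reader back to the table: "Dose modifications or discontinuations for patients experiencing QTc prolongations are summarized in" the Appendix B table above. Master protocol 4.9, adopted for Arm B by Appendix B 4.6, ends dosing for "Any AE that meets criteria for discontinuation as defined in the Dosing Modification and Toxicity Management Guidelines". Master protocol 6.2.3 asks for two further ECGs to confirm a QTcF above 470 ms or a shift of 60 ms or more.

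**The concern.** The same ECG finding leads to two different actions after recovery. Under 6.1.2 an investigator may restart AZD1775 at a lower dose. Under Table 9 the patient is finished with both drugs. Table 9 writes *Hold* where it means a temporary stop, so its discontinue rows cannot be read as a pause.

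What is at stake is patient safety, not the efficacy estimate. Appendix B 2.4.2 lists QT prolongation among the reported safety concerns for AZD1775 given with chemotherapy. A site working from the ECG section could, in good faith, rechallenge a patient whom the toxicity table takes off treatment.

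**Working it through.** The plan gives no figure to reproduce. The check sets the texts side by side and uses subtraction to show which patients are caught.

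**Step 1. The rules compared**

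| Finding | 6.1.2, AZD1775 | Table 9, AZD1775 | Table 9, carboplatin |
|---|---|---|---|
| QTc 450-480 ms (men), 470-480 ms (women) | Stop; may resume at reduced dose | Hold; resume one level lower | No change |
| QTc 481-500 ms | Stop; may resume at reduced dose | Hold; cardiologist | No change |
| QTc 501 ms or more | Stop; may resume at reduced dose | Discontinue | Discontinue |
| Shift of 60 ms or more | Stop; may resume at reduced dose | Discontinue | Discontinue |

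The first two rows are broadly compatible. The last two are not.

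**Step 2. Can the shift be the only 6.1.2 trigger?** Yes, if baseline plus 60 does not exceed the absolute limit:
- Men: 450 − 60 = 390, so baseline of 390 ms or less.
- Women: 470 − 60 = 410, so baseline of 410 ms or less.

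Worked case: a woman goes from 400 to 460 ms. The shift is 460 − 400 = 60 ms, and 460 is below 470, so the shift is her only trigger. Under 6.1.2 she may restart AZD1775; one level down in Appendix B Table 6 is 175 mg twice daily. In Table 9 she is below the 470-480 ms row for women, so the shift row alone applies and both drugs end.

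**Step 3. Can the 501 ms row apply without the shift?** Yes. 501 − 60 = 441, so with a baseline above 441 ms a QTc of 501 ms is a shift of less than 60 ms. Appendix B exclusion criterion 16 bars only a mean QTc above 470 ms. A woman entering at 470 ms who reaches 501 ms has shifted 501 − 470 = 31 ms. 6.1.2 still allows resumption; Table 9 does not.

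**Step 4. Carboplatin.** The scheduled ECG comes before dosing on Day 1 of each cycle. If AZD1775 is interrupted then, Appendix B 7.3 delays both drugs until the combination can resume, for up to 28 days unless the Study Physician approves continuing. So 6.1.2 read with 7.3 gives a delay of both drugs, while Table 9 ends both.

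**Step 5. Which text is meant to operate?** Section 7.3.2 is a direct instruction to use Table 9. Its exception covers unique toxicities noted after it, which does not reach back to 6.1.2, and 7.3.3.6 returns the reader to the table. Table 9 is therefore the operative rule, and 6.1.2 is the text that is wrong as written.

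**The case against.** The strongest reply is that the protocol already resolves this. Section 7.3.2 names Table 9 by number, and 6.1.2 is only permissive, so a site that discontinues breaks neither text. The resumption passage in 6.1.2 also ends with a reference to an Appendix B table whose number is not legible in the text available here. If that is Table 9, a reader who follows it meets the discontinue rows. Master protocol 6.2.3 asks for confirmatory ECGs, so one stray reading should not decide the matter. AZD1775 stops immediately under both texts.

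Most of this stands and limits the size of the point. It would be too strong to say that the protocol leaves two rules of equal standing. The unreadable table number should not be counted against the plan. What the reply does not remove is the permission itself: 6.1.2 tells a site that it can restart in two situations where the governing table says it cannot. Confirmatory ECGs establish that the shift is real; they do not settle what follows.

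A reader might also infer that Table 9 is inconsistent within itself, because a large shift can fall in a hold row and in the discontinue row together. The documents do not support that. Section 7.3.2 bases adjustments on the maximum non-hematologic toxicity, and 7.3 on the organ system with the greatest degree of toxicity, so the stricter row already applies.

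**Conclusion.** The point holds: the resumption sentence in Appendix B 6.1.2 is too wide. It permits rechallenge with AZD1775 after a shift of 60 ms or more, and after a QTc of 501 ms or more, where Table 9 permanently discontinues both drugs. Severity is minor to moderate. The texts agree on stopping AZD1775 at once and differ only after recovery. The protocol gives no frequency for such shifts, so the number of patients affected is unknown.

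A reader might infer that the conflict threatens the primary analysis. It does not: under master protocol 4.9.1, patients who stop for reasons other than progression stay in scheduled tumor assessment, and under 9.3.1 all treated patients are in the Full Analysis Set. Arm C uses similar stop-and-resume wording, but that shows no error in Arm B.

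The conclusion assumes that *Discontinue treatment* in Table 9 means a permanent stop, as its contrast with *Hold* indicates, and that Table 9 reflects the sponsor's clinical intent.

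**What to change.** In Appendix B 6.1.2, limit the resumption sentence to the cases where Table 9 leaves it open: QTc 450-480 ms in men or 470-480 ms in women, and 481-500 ms on cardiologist advice. Add that for a confirmed shift of 60 ms or more, or a QTc of 501 ms or more, both AZD1775 and carboplatin are discontinued according to Table 9. If the sponsor's safety physicians do intend rechallenge after a 60 ms shift, change that row of Table 9 instead. Table 9 needs no added rule for choosing between its rows.

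The cost is a few words in a protocol amendment or clarification letter, with no extra data and no extra patients.

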6.2 Pharmacokinetics

6.2.1 Collection of blood pharmacokinetic samples

Sparse PK samples will be collected for AZD1775 and CBDP during the study on Cycle 1 and at alternate cycles at the time points specified in [Appendix B Table](#) . The date and actual time of the PK sample will be recorded.

Appendix B Table 5 PKs: Carboplatin and AZD1775

	Cycle 1, Cycle 3 and beyond ^a			
	Day 1		Day 3 ^{a b}	
Timing	Predose	End of infusion	Pre-dose	2-4 hr
PK sample for Carboplatin	X	X		
PK samples for AZD1775			X	X

^a Alternate cycles (e.g Cycles, 3,5,7 etc.)

^b ± 15 minutes.

PK Pharmacokinetics

Samples will be collected, labelled, stored and shipped as detailed in the Laboratory Manual.

6.3 Efficacy Analysis

See Section 6.1 of the master protocol.

Efficacy in Arm B will be assessed using RECIST 1.1 criteria on images collected at baseline and then every 6 weeks ± 1 week until objective disease progression or off-study.

It is important to follow the assessment schedule as closely as possible (see [Appendix B Table 1](#)). If an unscheduled imaging assessment is performed and the patient has not progressed, every attempt should be made to perform the subsequent assessments at his or her next regularly scheduled imaging visit.

6.4 Biomarker analysis

Additional tumor based biomarkers that may be analyzed to investigate DNA damage/repair mechanisms related to AZD1775 include but are not limited to CCI [REDACTED]

Whole blood samples will be collected for CTC analysis at predose on Cycle 1 Day 1, Cycle 2 Day 1 and End of Treatment. Details for processing, handling, and shipping are provided in the Laboratory Manual.

In addition, select samples taken for collection of CCI [REDACTED] may be processed to generate circulating tumor DNA or blood samples may be collected in Streck DNA BCT tubes, and processed to isolate CCI [REDACTED]. Additional samples may be taken to generate circulating mRNA for storage and subsequent analyses. CCI [REDACTED]

7. SAFETY REPORTING AND MEDICAL MANAGEMENT

Please refer to Section 7 of the master protocol for details of reporting AEs, SAEs, AEs of special interest, paternal exposure, and management of investigational product (IP) related toxicities applicable to all arms in the study. Additional details for reporting AE, SAEs, AEs of special interest, paternal exposure, and management of IP-related toxicities applicable to Arm B are described below.

7.1 Reporting of adverse events

7.1.1 Time period for collection of adverse events

AEs and SAEs will be recorded from the time of informed consent, throughout the treatment period, and including the follow-up period (the follow-up period is 30 days after the last dose of study treatment of AZD1775 or CBDP). SAEs occurring in the follow-up period should be reported in the usual manner.

7.1.2 Follow-up of unresolved adverse events

Any AEs that are unresolved at the patient's last visit in the study are followed up by the Investigator for as long as medically indicated, but without further recording in the electronic case report form (eCRF). AstraZeneca retains the right to request additional information for any patient with ongoing AE(s)/SAE(s) at the end of the study, if judged necessary.

7.1.3 Reporting of serious adverse events

All SAEs must be reported, whether or not considered causally related to the IP or to the study procedure(s). All SAEs will be recorded in the eCRF.

If any SAE occurs in the course of the study, Investigators or other site personnel must inform appropriate AstraZeneca representatives immediately or no later than 24 hours of when he or she becomes aware of it.

For fatal or life-threatening AEs for which important or relevant information is missing, active follow-up is undertaken immediately. Investigators or other site personnel must inform AstraZeneca representatives of any follow-up information on a previously reported SAE within 1 calendar day (ie, immediately but no later than 24 hours of when he or she becomes aware of it).

In addition to standard SAE reporting process, the SCRI Innovations Safety Department will be notified about new SAE by sending automatic e-mail alert to SCRI Innovations SAE mailbox: [contact].

Automatic e-mail alert about follow-up information for SAEs and information on non-serious AEs that become serious should also be sent to SCRI Innovations Safety Department as soon as it is available.

The detailed SAE reporting process will be provided to the sites in the SAE reporting guidelines contained in the trial reference manual.

Investigators must report SAEs and follow-up information to their responsible Institutional Review Board (IRB) according to the policies of the responsible IRB. For fatal or life threatening AEs where important or relevant information is missing, active follow up is undertaken immediately.

AstraZeneca or their representative will provide Regulatory Authorities, Ethics Committees, and Principal Investigators with clinical safety updates/reports according to local requirements.

7.1.4 Post study events

After the patient has been permanently withdrawn from the study, there is no obligation for the Investigator to actively report information on new AEs or SAEs occurring in former study patients after the arm-designated- number of days, or 30-day safety follow-up period.

However, if an Investigator learns of any SAEs, including death, at any time after the patient has been permanently withdrawn from the study, and he/she considers there is a reasonable possibility that the event is related to the study treatment, the Investigator should notify AstraZeneca, Patient Safety, or its representative.

7.2 Pregnancy

7.2.1 Maternal exposure

If a patient becomes pregnant during the course of the study treatment should be discontinued immediately. Pregnancy itself is not regarded as an AE event unless there is a suspicion that the study treatment under investigation may have interfered with the effectiveness of a contraceptive medication. Congenital abnormalities/birth defects and spontaneous miscarriages should be reported and handled as SAEs. Elective abortions without complications should not be handled as AEs. The outcome of all pregnancies (spontaneous miscarriage, elective termination, ectopic pregnancy, normal birth, or congenital abnormality) should be followed up and documented even if the patient was discontinued from the study.

If any pregnancy occurs in the course of the study, the Investigator or other study center personnel must inform the appropriate AstraZeneca representatives within 1 calendar day (ie, immediately but no later than 24 hours of when he or she becomes aware of it).

The designated AstraZeneca representative works with the Investigator to ensure that all relevant information is provided to the AstraZeneca Patient Safety data entry site within 1 or 5 calendar days for SAEs, and within 30 days for all other pregnancies.

The same timelines apply when outcome information is available.

7.2.2 Paternal exposure

Pregnancy of the patient's partner is not considered to be an AE. However, the outcome of all pregnancies (spontaneous miscarriage, elective termination, ectopic pregnancy, normal birth, or congenital abnormality) should be followed up and documented if possible. To capture information about a pregnancy from the partner of a male patient, consent must be obtained from the male patient's partner to collect information related to the pregnancy and outcome; the male patient should not be asked to provide this information. The outcome of any conception occurring should be followed up and documented.

